### 2.4.2. Suggested Treatment Modification Guidelines for Maintenance Therapy

In the presence of lenalidomide-related non-hematologic toxicities (Table 2.4.2a), the study drug will be held until the toxicity resolves, then restarted at a reduced dose as described in Table 2.4.2b. Dose modifications for hematologic toxicities are described in Table 2.4.2c. If the patient is on DVT/PE prophylaxis or treatment, discontinuation or modifications of anticoagulation should be considered by the treating physician.

**Table 2.4.2a – Suggested Treatment Modification Guidelines for Long-Term Lenalidomide**

Grade by NCI CTCAE# 	Action
Non-blistering rash Grade 2-3 (Generalized rash ≥ 25% BSA)	Hold lenalidomide: Follow weekly. If the toxicity resolves to ≤ grade 1 restart lenalidomide at next lower dose level.
Non-blistering rash Grade 4	Discontinue lenalidomide.
Desquamating (blistering) rash any Grade	Discontinue lenalidomide.
Erythema multiforme ≥ Grade 3 (Severe (e.g., generalized rash or painful stomatitis); IV fluids, tube feedings, or TPN indicated)	Discontinue lenalidomide. If toxicity resolves to < grade 1 restart at next lower dose level.

Grade by NCI CTCAE# 	Action
Sinus bradycardia/ other cardiac arrhythmia Grade 2 (Non urgent, medical intervention indicated OR Moderate)	Hold lenalidomide. If the toxicity resolves to $\leq$ grade 1 restart lenalidomide at next lower dose level .
<math>\geq</math> Grade 3 (Incompletely controlled or controlled with device- e.g. pacemaker or Severe)	Discontinue lenalidomide. If toxicity resolves to $<$ grade 1 restart at next lower dose level.
Allergic reaction or hypersensitivity Grade 2-3 (flushing; urticaria; dyspnea; drug fever $\geq$ 38°C – symptomatic bronchospasm; parenteral meds indicated)	Hold lenalidomide If the toxicity resolves to $\leq$ grade 1 restart lenalidomide at next lower dose level.
Grade 4 (anaphylaxis)	Discontinue lenalidomide
Venous thrombosis/embolism <math>\geq</math> Grade 3 (DVT or cardiac thrombosis; intervention indicated)	Hold (interrupt) lenalidomide and start anticoagulation. Restart therapy per institutional guidelines.
Glomerular filtration rate (Creatinine Clearance) <math>\geq</math> Grade 3 ( $\leq$ 25%LLN, chronic dialysis not indicated)	Hold (interrupt) lenalidomide. If creatinine clearance has improved to $\leq$ grade 2 restart at next lower dose level.
Other non-hematologic toxicity assessed as Lenalidomide-related <math>\geq</math> Grade 3	Hold (interrupt) lenalidomide. If the toxicity resolves to $\leq$ grade 2 restart lenalidomide at next lower dose level.
Hyperthyroidism or Hypothyroidism	Hold lenalidomide. Evaluate etiology, and initiate appropriate therapy. Restart lenalidomide at next lower dose level.
Peripheral Neuropathy Grade 2 with pain or Grade 3	Hold lenalidomide. If the toxicity resolves to $<$ Grade 1 restart therapy at next lower dose level.
Peripheral Neuropathy Grade 4	Discontinue lenalidomide.
Constipation Grade 1-2	Initiate bowel regimen and maintain dose level.
Constipation <math>\geq</math> Grade 3	Hold lenalidomide. If the toxicity resolves to $\leq$ Grade 1 restart therapy at next lower dose level.
Pregnancy	Discontinue lenalidomide study drug.

Please consult NCI CTCAE version 3.0 <http://ctep.cancer.gov/reporting/> for complete **Grade** descriptions. The “ $\geq$  **Grade 3**” descriptions listed above are minimums

If a subject, or the partner of a male study subject, misses her period or if her pregnancy test or her menstrual bleeding is abnormal, pregnancy testing and counseling must be performed (Section 4.4.5).

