**Table 2.4.2b – Lenalidomide Dose Reduction Steps During Long-Term Maintenance Therapy**

Lenalidomide Dose Reduction Steps for Non-Hematologic Toxicity	
Dose at Time of Toxicity	Dose reduction
15 mg daily	10 mg daily
10 mg daily	5 mg daily
5 mg daily	5 mg daily for 21 days every 28 days
5 mg daily for 21 days every 28 days	Discontinue lenalidomide

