**2.4.3. Lenalidomide Maintenance Dose Re-escalation:**

If a dose reduction has occurred and ANC  $\geq$  1000/ $\mu$ L and platelet count is  $\geq$  75,000/ $\mu$ L, the study drug dose may be re-escalated as shown in Table 2.4.2b, one step per cycle to a maximum of 15 mg daily.

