### 4.3. Adverse Event Reporting

#### 4.3.1. Unexpected, Grades 3-5 Adverse Events

Reporting of Adverse Events (AE) in the long-term follow-up protocol will follow the same mechanism as the BMT CTN 0702 parent clinical trial for patients receiving long-term lenalidomide maintenance therapy. AEs will be reported according to the BMT CTN Manual of Procedures. The BMT CTN Data and Safety Monitoring Board (DSMB) will be responsible for the safety and oversight of this long-term follow-up protocol. Unexpected, grades 3-5 adverse events will be reported through the expedited AE reporting system in AdvantageEDC using NCI's Common Terminology Criteria for Adverse Events (CTCAE) Version 4.0. Unexpected, grade 4-5 AEs must be reported within 24 hours of knowledge of the event. Unexpected, grade 3 AEs must be reported within three business days of knowledge of the event.

The descriptions and grading scales found in the NCI Common Terminology Criteria for Adverse Events (CTCAE) Version 4.0 will be utilized for AE reporting and can be found at [http://evs.nci.nih.gov/ftp1/CTCAE/CTCAE\\_4.03\\_2010-06-14\\_QuickReference\\_5x7.pdf](http://evs.nci.nih.gov/ftp1/CTCAE/CTCAE_4.03_2010-06-14_QuickReference_5x7.pdf).

Selected expected serious AEs (Appendix F - Table F-1) require expedited reporting with an Individual Case Safety Report (ICSR). Additionally, selected AEs of interest (Appendix F - Table F-2) will require expedited reporting through an ICSR, if they fulfill serious criteria according to the Code of Federal Regulations Title 21 (21 CFR 312.32) and occur after the administration of lenalidomide and up to 30 days after the permanent discontinuation of lenalidomide. See Appendix F for additional details on expedited reporting.

The aforementioned adverse event reporting criteria are for patients who receive long-term lenalidomide maintenance therapy. Patients not eligible for receiving long-term lenalidomide maintenance therapy or patients who have permanently discontinued lenalidomide maintenance will not require reporting of unexpected grades 3-5 adverse events or ICSRs with the exception of second primary malignancies as noted in 4.3.2. All patients will be required to report deaths as noted in section 4.3.3.

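### Two severe-toxicity rows of the lenalidomide table say both discontinue and restart, and re-escalation after a non-hematologic dose reduction depends on blood counts alone

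*Protocol*

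**What the plan says.** - **Protocol Table 2.4.2a.** For erythema multiforme of grade 3 or more the action is "Discontinue lenalidomide. If toxicity resolves to < grade 1 restart at next lower dose level". The row for sinus bradycardia or other cardiac arrhythmia of grade 3 or more carries the same instruction.
- **Same table, other rows.** The row "Desquamating (blistering) rash any Grade" ends in discontinuation with no restart. The pregnancy row says "Discontinue lenalidomide study drug" and nothing more.
- **Protocol Section 2.4.2, lead-in to the table.** For lenalidomide-related non-hematologic toxicities, "the study drug will be held until the toxicity resolves, then restarted at a reduced dose as described in Table 2.4.2b".
- **Protocol Section 2.4.3.** Once a dose has been reduced, and provided ANC is at least 1000/µL and platelets at least 75,000/µL, "the study drug dose may be re-escalated as shown in Table 2.4.2b, one step per cycle to a maximum of 15 mg daily". Table 2.4.2b is headed "Lenalidomide Dose Reduction Steps for Non-Hematologic Toxicity". SAP Section 1.4 repeats both the lead-in and the re-escalation rule, referring to the protocol for detail.
- **Grading versions.** The footnote to Table 2.4.2a says "Please consult NCI CTCAE version 3.0". Protocol Section 4.3.1 has adverse events reported "using NCI's Common Terminology Criteria for Adverse Events (CTCAE) Version 4.0".

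**The concern.** A modification table works only if its verbs have fixed meanings. In most of Table 2.4.2a they appear to: 'Hold' is followed by a way back, and 'Discontinue' stands alone. Two cells for severe toxicity break that pattern. One site could stop a patient for good while another rechallenges a patient with the same event, each relying on the same cell.

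The re-escalation rule raises a different problem. It applies after any reduction, but its only conditions are blood counts. A patient whose dose was lowered for neuropathy or rash satisfies it on counts that say nothing about the neuropathy or the rash.

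What is at stake is mainly patient safety and uniform conduct across sites. Some record-keeping also turns on whether a stop counts as temporary or permanent: the follow-up schedule that applies, and the point at which adverse-event reporting ends.

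**Working it through.** No arithmetic beyond counting applies, so the check sets the passages side by side.

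**1. Verbs in Table 2.4.2a.** The table has 17 action cells:

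| Instruction | Rows | Count |
|---|---|---|
| Hold, with a way to restart | non-blistering rash gr 2-3; arrhythmia gr 2; allergic reaction gr 2-3; venous thrombosis; creatinine clearance; other non-hematologic; thyroid; neuropathy gr 2 with pain or gr 3; constipation gr 3 or more | 9 |
| Discontinue, no restart | non-blistering rash gr 4; blistering rash any grade; allergic reaction gr 4; neuropathy gr 4; pregnancy | 5 |
| Discontinue, then restart | erythema multiforme gr 3 or more; arrhythmia gr 3 or more | 2 |
| Maintain dose | constipation gr 1-2 | 1 |

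9 + 5 + 2 + 1 = 17. The two mixed cells require resolution to below grade 1 before restart. The neuropathy row (grade 2 with pain, or grade 3) sets the same threshold but says 'Hold'. The change of verb therefore cannot be explained by a stricter restart threshold.

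**2. Does the surrounding text settle it?** The lead-in has non-hematologic toxicities held and restarted. Taken literally, it contradicts the five stop-only rows, so it cannot be the governing reading for the two mixed ones. Usage elsewhere is also mixed. Appendix B, on pregnancy testing during the study, uses 'discontinued' for a pause while an abnormal result is evaluated. Sections 4.3.1 and 4.3.2.1 add 'permanently' or 'permanent' when they mean a final stop.

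**3. Row overlap.** Nothing says which row governs an erythema multiforme that blisters. One row has a restart and the other does not. Appendix F Table F-1 lists erythema multiforme together with toxic epidermal necrolysis, which makes the overlap plausible.

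**4. Re-escalation, followed as written.** Take a patient on 10 mg daily with grade 3 neuropathy:
- Table 2.4.2a: hold, then restart at the next lower level once the grade is below 1.
- Table 2.4.2b: the next lower level is 5 mg daily.
- Section 2.4.3: a reduction has occurred, so with ANC at least 1000/µL and platelets at least 75,000/µL the dose may rise one step per cycle, back to 10 mg. Neuropathy is not mentioned.

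For two rows (creatinine clearance and other non-hematologic toxicity) restart is allowed at grade 2 or below. There the count-only condition can be met while some of the toxicity persists. For a reduction made for low counts, the condition does match the cause.

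**5. What turns on the reading.**
- *Schedule.* Section 2.4.1 sends patients who discontinue to the schedule in Section 4.4.1, which lists no pregnancy tests or blood counts. Section 4.4.2 requires pregnancy tests in women of childbearing potential to continue through breaks in therapy, and a blood count before each monthly supply.
- *Safety reporting.* Section 4.3.1 ends reporting of unexpected grade 3-5 events, second malignancies excepted, once lenalidomide is permanently discontinued.
- *Analysis.* SAP Section 4.1 uses discontinuation as a time-varying covariate. Exhibit 07LT-4B calls it permanent discontinuation. The primary stratified log-rank test does not use it.

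**The case against.** The strongest reply is that the two cells describe a sequence: stop, then restart if a condition is met. The protocol never defines 'Discontinue' as final, and Appendix B uses it for a pause. That reading is available, and it may be the intended one. It does not remove the problem, because five rows of the same table use the word alone and the neuropathy row uses 'Hold' for the same threshold.

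Several further points stand and limit the concern:
- Section 2.4.2 and Table 2.4.2a are headed as suggested guidelines, so some variation between sites is expected anyway.
- Re-escalation is permissive. The ladder in Table 2.4.2b matches the one in Table 2.4.2c, so the cross-reference works as a list of steps. Seven of the nine hold rows already require improvement to a stated grade before restart. The fault is a missing condition, not a contradiction.
- The erythema multiforme row describes generalized rash or painful stomatitis and does not mention blisters. Whether the rows overlap in practice is a clinical judgement.

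A reader might also infer that the two CTCAE versions contradict each other. They do not: version 3.0 supplies the grades for dose modification and version 4.0 those for adverse-event reporting. One event could carry two grades, which deserves a sentence of explanation, but no site is given two versions for one dosing decision.

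A reader might likewise infer that the SAP's discontinuation covariate is corrupted. The exhibit specifies permanent discontinuation, and a patient who restarts has not permanently discontinued, whatever verb the table used. The SAP also already flags that model as limited in interpretation.

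**Conclusion.** The concern holds in a bounded form. Two of 17 action cells, both for severe toxicity, can be read as a final stop or as an interruption; the lead-in conflicts with five other rows; and an erythema multiforme that blisters could fall under two rows with different instructions. Section 2.4.3, as written, lets a dose reduced for a non-hematologic toxicity rise again on blood counts alone.

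Only the two cells and the rash overlap could lead sites to manage the same event in opposite ways. It would be tempting to extend that to the re-escalation rule and the CTCAE versions, but the first is an optional step lacking a condition and the second serves two separate purposes.

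The number of patients affected cannot be derived from the documents. The effect on the secondary and supplemental models is probably small, and the primary comparison of randomized arms is unaffected. The case for acting rests on patient safety, on the choice between the Section 4.4.1 and 4.4.2 schedules, and on when adverse-event reporting stops. It assumes that sites follow the table as printed, with no clarifying instruction outside these documents.

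**What to change.** The sponsor's clinical team should reconcile, without any rule being proposed here:

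1. the two mixed cells of Table 2.4.2a with the rest of the table, and the erythema multiforme row with the blistering-rash row;
2. the lead-in in Section 2.4.2 with the rows that allow no restart;
3. Section 2.4.3 with Tables 2.4.2a and 2.4.2b, stating how re-escalation applies after a non-hematologic reduction;
4. SAP Section 1.4 with whatever results.

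The text should use one term for a hold and another for a permanent discontinuation throughout, so that sites record stops in the same way. The case report forms are not among the documents, so check first whether they already make this distinction. A sentence explaining the use of two CTCAE versions would be a useful side note.

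The cost is a clarification memo or amendment text. Reconciling the wording in itself calls for no new visits, sample size or analysis.

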**Table 2.4.2b – Lenalidomide Dose Reduction Steps During Long-Term Maintenance Therapy**

Lenalidomide Dose Reduction Steps for Non-Hematologic Toxicity	
Dose at Time of Toxicity	Dose reduction
15 mg daily	10 mg daily
10 mg daily	5 mg daily
5 mg daily	5 mg daily for 21 days every 28 days
5 mg daily for 21 days every 28 days	Discontinue lenalidomide

**Table 2.4.2c – Lenalidomide Dose Modifications for Hematologic Toxicities**

Lenalidomide Dose Modifications for Hematologic Toxicities	
Dose at Time of Toxicity	Action
15 mg per day	If ANC is < 1000/ $\mu$ L or the platelet count is < 50,000/ $\mu$ L, then lenalidomide will be held for up to 8 weeks. Lenalidomide drug may be re-instituted at 10 mg per day once the ANC is $\geq$ 1000/ $\mu$ L and the platelet count is $\geq$ 50,000/ $\mu$ L. If, however, after an 8 week treatment delay, the ANC remains < 1000/ $\mu$ L or the platelet count < 50,000/ $\mu$ L, maintenance therapy will be discontinued.
10 mg per day	If ANC is < 1000/ $\mu$ L or the platelet count is < 50,000/ $\mu$ L, then lenalidomide will be held for up to 8 weeks. Lenalidomide may be re-instituted at 5 mg per day once the ANC is $\geq$ 1000/ $\mu$ L and the platelet count is $\geq$ 50,000/ $\mu$ L. If however, after an 8 week treatment delay, the ANC remains < 1000/ $\mu$ L or the platelet count < 50,000/ $\mu$ L, maintenance therapy will be discontinued.
5 mg per day	If ANC is < 1000/ $\mu$ L or the platelet count is < 50,000/ $\mu$ L, then lenalidomide will be held for up to 8 weeks. Once the ANC is $\geq$ 1000/ $\mu$ L and the platelet count is $\geq$ 50,000/ $\mu$ L, then lenalidomide may be re-instituted at 5 mg per day for 21 days of a 28-day cycle. If, however, after an 8 week treatment delay, the ANC remains < 1000/ $\mu$ L or the platelet count < 50,000/ $\mu$ L, maintenance therapy will be discontinued.
5 mg per day for 21 of 28 days	If ANC is < 1000/ $\mu$ L or the platelet count is < 50,000/ $\mu$ L, then maintenance therapy will be discontinued.

**2.4.3. Lenalidomide Maintenance Dose Re-escalation:**

If a dose reduction has occurred and ANC  $\geq$  1000/ $\mu$ L and platelet count is  $\geq$  75,000/ $\mu$ L, the study drug dose may be re-escalated as shown in Table 2.4.2b, one step per cycle to a maximum of 15 mg daily.

## 2.5. Supportive Care

### 2.5.1. Deep Vein Thrombosis (DVT) and Pulmonary Embolism (PE) Prophylaxis

Patients receiving dexamethasone and thalidomide as remission induction therapy for MM have an increased risk of developing DVT/PE. This risk may be as high as 10%. It is unclear whether the risk is the same in patients receiving lenalidomide as a single agent and as maintenance therapy after autologous transplantation. Treating physicians should be aware of this risk and have heightened vigilance regarding this possible toxicity. Aspirin should be administered per institutional guidelines during lenalidomide maintenance therapy unless the patient is treated with alternate prophylaxis of either low molecular weight heparin or coumadin.

## 2.6. Participant Risks

### 2.6.1. Lenalidomide

Common toxicities described for lenalidomide include:

- Neurologic: Somnolence, dizziness, headache, confusion, tremor, loss of co-ordination, asthenia, paresthesia, numbness, and leukoencephalopathy (radiographic findings).
- Hematologic: anemia, neutropenia, leucopenia, lymphopenia and thrombocytopenia; thromboembolic events (deep vein thrombosis and pulmonary embolism).
- Gastrointestinal: Constipation, dehydration, dry mouth, diarrhea, dyspepsia, nausea, vomiting and stomatitis.
- Constitutional: Weakness, insomnia, rigors, chills, sweating, weight loss and fever.
- Reproductive: teratogenicity and miscarriage.
- Musculoskeletal: arthralgia, back/neck pain, joint pain, muscle cramp and weakness.
- Cardiac: hypotension.
- Dermatologic: rash, dry skin, itching.
- Endocrine: hypothyroidism.
- Infection.
- Pulmonary: cough, dyspnea.
- Metabolic: hypokalemia, liver damage.
- Renal: increased creatinine, renal failure.

### **Pregnancy reporting:**

See Section 4.2.3, Adverse Event Reporting.

**Other instructions related to lenalidomide:**

Only one cycle of therapy may be dispensed to the patient each month. During long-term lenalidomide maintenance, a maximum 28-day supply may be dispensed. Lenalidomide capsules should be swallowed whole, and should not be broken, chewed or opened. If a dose of lenalidomide is missed, it should be taken as soon as possible on the same day. If it is missed for the entire day, it should not be made up. Patients taking more than the prescribed dose of lenalidomide should be instructed to seek emergency medical care if needed and contact study staff immediately.

**2.7. Study Drug Supply****2.7.1. Lenalidomide (NSC 703813)**

**Lenalidomide will be provided by Celgene and distributed by Biologics, Incorporated. Patients must be registered in the Revlimid REMS® program (formerly RevAssist® for Study Participants (RASP) program) in order to receive lenalidomide through the program (please see Appendix C).**

**NOTE:**

**Before lenalidomide is dispensed, patients must 1) have a negative pregnancy test (if applicable) and 2) be counseled by a trained counselor. BMT CTN 0702 Long-Term Follow-Up Study patients must be counseled through the Revlimid REMS® program. A maximum 28-day supply may be dispensed to a patient at one time.**

**Chemical Name:** 3-(4'-amino-1,3-dihydro-1-oxo-2*H*-isoindol-2-yl)-2,6-piperidinedione

**Other Names:** CC-5013, Revlimid®, CDC-501

**Classification:** Immunomodulatory Agent

**CAS Registry Number:** 191732-72-6

**Molecular Formula:** C13H13N3O3

**M.W.:** 259.25

**Mechanism of Action:**

Lenalidomide, a thalidomide analog, is an immunomodulatory agent with a spectrum of activity that is still under investigation. Some of its effects include inhibition of inflammation, inhibition of angiogenesis, inhibition of hematopoietic tumor cell proliferation, modulation of stem cell differentiation and up regulating responses of T cells and NK cells.

**Drug Supply and Storage:**

Celgene supplies and Biologics, Inc. distributes lenalidomide 5 mg (size 2) hard gelatin capsules in tamper-evident, child-resistant, opaque, high density polyethylene (HDPE) bottles with HDPE caps.

The capsules also contain anhydrous lactose, microcrystalline cellulose, croscarmellose sodium, and magnesium stearate.

Lenalidomide (Revlimid®) will be provided to research subjects for the duration of their participation in this trial at no charge to them or their insurance providers. Lenalidomide will be provided in accordance with the Revlimid REMS® program of Celgene Corporation. Per standard Revlimid REMS® requirements all physicians who prescribe lenalidomide for research subjects enrolled into this trial, and all research subjects enrolled into this trial, must be registered in and must comply with all requirements of the Revlimid REMS® program. Prescriptions must be filled within 7 days.

All study participants must be registered into the mandatory Revlimid REMS® program, and be willing and able to comply with the requirements of the Revlimid REMS® program including counseling and phone surveys.

Any unused lenalidomide supplies distributed through the Revlimid REMS® program must be returned as instructed through the Revlimid REMS® program.

**Administration:**

Take lenalidomide by mouth with or without food. Do not crush, chew or open capsules.

**Dispensing:**

Only enough lenalidomide for one cycle may be dispensed at one time. The drug will be mailed directly to the patient through the Revlimid REMS® program.

**Patient Care Implications and Counseling:**

Risks Associated with Pregnancy

Lenalidomide is structurally related to thalidomide. Thalidomide is a known human teratogenic active substance that causes severe life-threatening birth defects. An embryofetal development study in animals indicates that lenalidomide produced malformations in the offspring of female monkeys who received the drug during pregnancy. The teratogenic effect of lenalidomide in humans cannot be ruled out. Therefore, a risk minimization plan to prevent pregnancy must be observed.

Definition of female of childbearing potential (FCBP)

This protocol defines a female of childbearing potential as a sexually mature female who: 1) has not undergone a hysterectomy or bilateral oophorectomy or 2) has not been naturally postmenopausal (amenorrhea following cancer therapy does not rule out childbearing potential) for at least 24 consecutive months (i.e., has had menses at any time in the preceding 24 consecutive months).

Before starting study drug:

Female Subjects:

- FCBP must have two negative pregnancy tests (minimum sensitivity of 50 mIU/mL) prior to starting study drug. The first pregnancy test must be performed within 10-14

days prior to the start of study drug and the second pregnancy test must be performed within 24 hours prior to the start of study drug (prescriptions must be filled within 7 days as required by Revlimid REMS®). The subject may not receive study drug until the Investigator has verified that the results of these pregnancy tests are negative.

- FCBP must either commit to continued abstinence from heterosexual intercourse or begin TWO acceptable methods of birth control, one highly effective method and one additional effective method AT THE SAME TIME, at least 4 weeks before starting lenalidomide. FCBP must also agree to ongoing pregnancy testing.

Male Subjects:

- Must agree to use a latex condom during sexual contact with females of childbearing potential while participating in the study and for at least 28 days following discontinuation from the study even if he has undergone a successful vasectomy.

All Subjects:

- Only enough lenalidomide for one cycle of therapy may be dispensed with each cycle of therapy.
- If pregnancy or a positive pregnancy test does occur in a study subject or the partner of a male study subject during study participation, lenalidomide must be immediately discontinued.

Counseling Requirements for the Revlimid REMS® program:

- This program provides education and counseling on the risks of fetal exposure, blood clots and reduced blood counts. Counseling will be provided by Biologics, Inc. prior to drug distribution please refer to Appendix C (Revlimid REMS® Program). Patients will be required to receive counseling every 28 days during treatment with lenalidomide, follow the pregnancy testing and birth control requirements of the program that are appropriate and take telephone surveys regarding compliance with the program.

